#### **8.4.2 Study Stopping Rule**

If any subject experiences a life-threatening AE (Grade 4) that is considered to be related to study drug, further dosing in all enrolled subjects will be suspended until the DEC has evaluated the event and determined the appropriate course of action. At any time during the study, the study may be discontinued if the DEC determines that further drug exposure would pose an undue risk to subjects.

#### **8.4.3 Individual Stopping Rule**

Dosing for any individual subject will be discontinued (i.e., no further study drug will be given to that subject) if the subject experiences any study drug-related SAE or any study drug-related non-SAE adverse event that, in the judgement of the Investigator and Medical Monitor suggest that it could be unsafe to administer further study drug to that subject. Additionally, a subject may be discontinued from further treatment with study drug, at the discretion of the Investigator with consultation with the Medical Monitor, if they require a significant increase in dose(s) of anti-pemphigus medication(s) for the management of pemphigus.

## 9 STUDY DRUG

For detailed information regarding SYNT001 preparation and administration, refer to the Pharmacy Manual.

### 9.1 SYNT001

SYNT001 is provided in vials containing 5 mL SYNT001 (extractable volume) at a nominal concentration of 50 mg/mL. The product is supplied as a liquid at pH  $6.5 \pm 0.5$ . SYNT001 is diluted in Dextrose 5% in Water (D5W) to prepare the solution for infusion. SYNT001 will be infused via IV in 250 mL over 1 hour using a 0.2-micron, inline filter.

Two cohorts of 8 eligible subjects each will receive 5 once-weekly 60-minute infusions of SYNT001 in planned doses of 10 mg/kg or 30 mg/kg. Based on review of safety, PD, and clinical outcomes of these two cohorts, a third cohort of up to 8 subjects may be treated at another dose, with a maximum dose of 45 mg/kg, but may also be lower than 10 mg/kg or between 10 and 30 mg/kg, inclusive.

The specification for host cell DNA in SYNT001 is  $< 2$  pg/mg, the limit of quantitation of the assay. To comply with regulatory guidelines, which specify a maximum level of 10 ng host cell DNA per dose, dosing is limited to 5000 mg of SYNT001. Therefore, at the highest dose possible in this study (45 mg/kg), maximum subject weight will be limited to 111 kg.

### 9.2 Cohort Dosing

Cohorts will be dosed sequentially beginning with Cohort 1. The first 2 subjects will be dosed at least 24 hours apart. A review of the 24-hour safety data for the first subject will be performed to ensure that there are no overt safety concerns before dosing the second subject. A review of the 7-day safety data for the first 2 subjects will be performed prior to dosing the remaining 6 subjects in the cohort. Cohort 2, and Cohort 3 if added, will be dosed per the same schedule

### 9.3 Timing of Dosing

On Days 0, 7, 14, 21, and 28, subjects will receive a 60-minute IV infusion of SYNT001 in the morning. The date and time the dose is administered will be recorded.

### 9.4 Identity of Investigational Products

All supplies of SYNT001 will be supplied by Syntimmune and must be stored refrigerated (2°C to 8°C/36°F to 46°F) in the carton and protected from light, in a securely locked area, accessible to authorized persons only, until needed for dose preparation. Qualified site personnel will

inventory the investigational product received and will maintain records of disposition of the drug, including dates, quantity and use.

### **9.5 Investigational Product Retention at Study Site**

The Investigator (or designee) is responsible for maintaining accurate accountability records of the investigational product throughout the clinical study. All study drug received at the site must be inventoried and accounted for in an accountability log provided by the Sponsor. All dispensing and accountability records will be available for Sponsor review. Study drug accountability will be verified during on-site monitoring visits.

Upon the completion or termination of the study, and upon written authorization from the Sponsor, or its representative, all unused and/or partially used study drug should be returned or destroyed at the investigational site, as specified by Sponsor. It is the Investigator's responsibility to ensure that the Sponsor, or its representative, has provided written authorization that procedures for proper disposal of the study drug have been established, and that appropriate records of the disposal are documented and maintained. No unused study drug may be disposed until fully accounted for by the Sponsor monitor (or designee)

### **9.6 Warnings and Precautions**

**Note:** Subjects must not receive any vaccinations from within 2 weeks of screening until 2 months after the last dose of study drug.

#### **9.6.1 Infusion Reaction**

SYNT001 will be given as an IV infusion over 1 hour. As with all mAbs administered by IV infusion, infusion reactions are possible. In nonclinical testing of SYNT001 in NHPs, clinical observations were limited to infusion reactions due to the immunogenicity of SYNT001 in NHPs. These reactions included transient emesis/vomitus which typically occurred within 1 hour of dosing at all dose groups, but only after the third weekly infusion following the development of ADAs. Transient histamine-type responses were noted 30 minutes post-dose in some animals in all dose groups, but only following the third weekly infusion as above. These reactions were consistent with a histamine reaction (decreased activity, periocular swelling, erythema, facial flushing, eyelids partially/completely closed, and/or generalized weakness). With the exception of vomitus/emesis and red skin discoloration associated with injection or blood draw sites, these observations spontaneously resolved within 1-hour post-dose. Subsequent pretreatment with intramuscular diphenhydramine prevented further histamine-type reactions. All doses of SYNT001 were administered by bolus infusion over approximately 5 minutes in the NHP

studies. However, all of the observed infusion reactions (including vomitus/emesis and histamine-type reactions) associated with ADAs are not at all predictive of what may occur in humans [Bugelski 2004, Ponce 2009] and furthermore, are not considered relevant to predicting responses in humans [ICH S6(R1) 2011].

Typically, infusion reactions to monoclonal antibodies observed in human studies develop within 30 minutes to 2 hours after the initiation of drug infusion, although symptoms may be delayed for up to 24 hours. Most are mild in severity, although severe and even fatal reactions can occur.

[figure not shown]
### **Guidelines for Grading and Management of Allergic or Infusion-Related Reactions**

Allergic and/or infusion-related reactions include hypersensitivity reactions and cytokine release syndromes. These reactions are experienced by patients during or within hours of the infusion of monoclonal antibody therapy. Symptoms can include flushing, alterations in heart rate and blood pressure, dyspnea, bronchospasm, back pain, fever, urticaria, edema, nausea, and all types of rashes. Anaphylaxis is recognized as a severe, life-threatening, generalized, or systemic reaction. This is a medical emergency characterized by rapidly developing life-threatening airway and/or breathing and/or circulation problems usually associated with skin or mucosal changes.

[figure not shown]
Management of Grade 1 infusion reactions include decreasing the rate of infusion by 50% and observing. Symptoms may also be treated as needed with medications such as diphenhydramine, hydrocortisone or acetaminophen.

Management of Grade 2 and higher infusion reactions should include stopping the infusion of study drug. See [Figure 1](#) and [Figure 2](#) for details on the management of Grades 1-2 and Grade 3 or higher infusion reactions. The severity of and management of allergic or infusion-related reactions will be graded and managed using NCI CTCAE Version 4.03 (see [Table 5](#)).

**Figure 1: Management of Mild (Grade 1) to Moderate (Grade 2) Infusion Reactions**

**Figure 2: Management of Severe (Grade 3 or higher) Infusion Reactions**

**Table 5: Grading and Management of Allergic or Infusion-Related Reactions**

Adverse Event	Grade				
	1	2	3	4	5
Infusion-Related Reaction	Mild transient reaction; infusion interruption not indicated; intervention not indicated	Therapy or infusion interruption indicated but responds promptly to symptomatic treatment (e.g., antihistamines, NSAIDs, narcotics, IV fluids); prophylactic medications indicated for ≤ 24 hours	Prolonged (e.g., not rapidly responsive to symptomatic medication and/or brief interruption of infusion); recurrence of symptoms following initial improvement, hospitalization indicated for clinical sequelae	Life-threatening consequences; urgent intervention required	Death
Allergic Reaction	Transient flushing or rash, drug fever < 38.0°C. Intervention not indicated	Therapy or infusion interruption indicated but responds promptly to symptomatic treatment (e.g., antihistamines, NSAIDs, narcotics, IV fluids); prophylactic medications indicated for ≤ 24 hours	Prolonged (e.g., not rapidly responsive to symptomatic medication and/or brief interruption of infusion); recurrence of symptoms following initial improvement, hospitalization indicated for clinical sequelae (e.g., renal impairment, pulmonary infiltrates)	Life-threatening consequences; urgent intervention required	Death
Anaphylaxis	-	-	Symptomatic bronchospasm, with or without urticarial; parenteral intervention indicated; allergy-related edema/angioedema; hypotension	Life-threatening consequences; urgent intervention required	Death
Cytokine release syndrome	Mild reaction; infusion interruption not indicated; intervention not indicated	Therapy or infusion interruption indicated but responds promptly to symptomatic treatment (e.g., antihistamines, NSAIDs, narcotics, IV fluids); prophylactic medications indicated for ≤ 24 hours	Prolonged (e.g., not rapidly responsive to symptomatic medication and/or brief interruption of infusion); recurrence of symptoms following initial improvement, hospitalization indicated for clinical sequelae (e.g., renal impairment, pulmonary infiltrates)	Life-threatening consequences; pressor or ventilator support indicated	Death

Abstracted from NCI CTCAE Version 4.03.

### 9.6.2 Potential Immune Effects

An antibody blocking FcRn is anticipated to have several effects. These include acceleration of catabolism of IgG, but not other immunoglobulin isotypes such as IgA and IgM, leading to dose-dependent decreases in circulating IgG levels by up to an estimated 50% from the baseline levels after a single dose and further decreases after multiple doses up to a 70% to 80% reduction. Based on studies in humans, it is expected that with a single dose, the nadir of this effect will occur approximately 5 days after dosing. The time course of recovery of IgG following dosing in the Phase 1a study suggests that a return to within normal limits occurs within 4 weeks after a single dose and within 4 weeks after multiple doses as shown in NHPs.

Given the normal adult range of IgG of 700 to 1600 mg/dL (in some references), with a mean of 1150 mg/dL, a 50% decrease in the mean would be to 575 mg/dL and a 50% decrease from the low end of the normal range of 700 mg/dL would be to 350 mg/dL. An 80% decrease from baseline after multiple doses would result in IgG levels of 230 mg/dL and 140 mg/dL, respectively. While these levels are in the range found in patients with primary humoral immunodeficiency [[Ameratunga 2013](#)], the levels will be transient. Study subjects will be monitored clinically for any infection. Further, commercial IVIG can be given to reverse the low IgG levels in case of a bacterial infection occurring while their IgG levels are decreased.

An antibody blocking FcRn is expected to also down modulate innate and adaptive immunity and the catabolism of IgG-containing immune complexes (IC). Specifically, it is expected that anti-FcRn will promote the clearance of IgG-containing ICs and the effects of these IC on stimulating innate immune cell production of inflammatory cytokines (e.g., IL-12, interferon- $\gamma$ , and tumor necrosis factor [TNF]) and inhibit the processing and presentation of antigens contained within IC and thus the antigen-specific activation of CD4+ and CD8+ T-cells. Therefore, subjects with pre-existing conditions that are dependent upon IgG antibodies, such as chronic infections (e.g., HIV, HBV or HCV), will be excluded from this study, as will subjects with active infection in general.

SYNT001 administration could decrease the level of protective antibodies from prior vaccinations. Protective antibody levels for tetanus and varicella-zoster virus (chickenpox) are to be tested in accordance with [Section 6.7.3](#).

## 10 CONCOMITANT MEDICATION AND TREATMENT

All treatments a subject receives within 14 days prior to enrollment through the end of the study (Day 56) will be documented. Concomitant medication and treatment for co-existing conditions, including those for pemphigus, are permitted if not excluded below. Topical antibiotics are permitted to treat active infections that occur on study. Topical or systemic treatments for oral candidiasis are permitted. Topical lidocaine for transient pain relief is acceptable as needed. Significant increases in anti-pemphigus medications may result in subjects being discontinued from the study. Concomitant treatment that is medically indicated for any AEs the subject experiences during the study are permitted

Use of the following treatments will not be permitted during the study unless otherwise specified:

- Rituximab or other anti-CD20 antibody
- Monoclonal antibodies other than study drug
- Any immunosuppressive drugs apart from corticosteroids, azathioprine, mycophenolate mofetil, or cyclosporine.
- Topical steroids
- Any dietary herbal supplements
- Any investigational drug or device
- Any vaccinations

If over a period of at least two weeks on study drug, a subject on corticosteroids shows the absence of new lesions and significant healing of lesions that existed at study baseline, a slow corticosteroid taper may be started as per the following suggested schedule

- If on > 30 mg of prednisone per day, decrease by 10 mg every two weeks until a dose of 30 mg per day then decrease by 5 mg every two weeks
- If on < 30 mg of prednisone per day, decrease by 5 mg every two weeks

In cases in which concomitant medications are used, details to be recorded include the following: medication name, start date and time, stop date and time, dose, route, frequency, and reason for use. The concomitant medication names are to be coded using the World Health Organization

(WHO) Drug Dictionary (WHO-DD March 2013, Type B2 or later) and classified by anatomical therapeutic chemical (ATC) categories.

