	
Exclusion criteria:
 
Subjects meeting any of the following criteria are to be excluded:
 
 
1. Subject unable or unwilling to comply with the protocol;
 
2. Active non-hematologic malignancy or history of non-hematologic malignancy in the 3 years prior to screening (exclusive of non-melanoma skin cancer and cervical cancer in situ);
 
3. Positive for HIV or hepatitis C antibody;
 
4. Positive for hepatitis B surface antigen;
 
5. Active infection or history of recurrent infections;
 
6. IVIG use within 60 days of screening;
 
7. Received any cytotoxic (other than azathioprine) or mAb therapy in the 3 months prior to screening;
 
8. Any exposure to an investigational drug or device within the 30 days prior to screening
 
9. Plasmapheresis or immunoadsorption within 60 days of screening
 

	
10. Cellular therapy at any time prior to screening
 
11. Use of any immunosuppressive drugs apart from corticosteroids, azathioprine, mycophenolate mofetil, or cyclosporine within 3 months of screening
 
12. Serum total IgG < 600 mg/dL;
 
13. Subject has any current medical condition that, in the opinion of the Investigator, may compromise their safety or compliance, preclude successful conduct of the study, or interfere with interpretation of the results (e.g., a significant pre-existing illness or other major comorbidity that the Investigator considers may confound the interpretation of the study results);
 
14. Any vaccination within 2 weeks of screening

Study drug, dosage, and administration	
SYNT001
 
Doses: 10 mg/kg and 30 mg/kg. A third cohort of up to 8 subjects may be treated at another dose, with a maximum dose of 45 mg/kg, but may also be lower than 10 mg/kg or between 10 and 30 mg/kg, inclusive.
 
SYNT001 is provided as a liquid at a nominal concentration of 50 mg/mL. SYNT001 is diluted in Dextrose 5% in Water (D5W) to prepare the solution for infusion.
 
Route of administration: IV in 250 mL over 1 hour

Control, dose, and route of administration	
Not applicable

Duration of subject participation and duration of study	
Up to 70 days (10 weeks): Screening of up to 2 weeks (14 days); dosing period of 4 weeks (28 days); and 4 weeks (28 days) of follow-up

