**Table 1: Study Assessments**

Timepoint (Study Day)	Screen -14 to -1	0	1 (±1 hr)	2 (± 2 hr)	5 p (±4 hr)	7 (±4 hr)	12 p (±6 hr)	14 (±6 hr)	19 p (±6 hr)	21 (±6 hr)	28 (±6 hr)	29 (±1 hr)	30 (±2 hr)	33 (±4 hr)	42 (±3 day)	Follow-Up 56 (±5 days) or ET Visit	Extended Follow- up q
Informed Consent	X																
Demographics/Medical History	X																
Inclusion/Exclusion	X																
Physical Examination a	X	X				X		X		X	X				X	X	
Vital Signs b	X	X	X	X	X	X	X	X	X	X	X	X	X	X	X	X	
Pulse Oximetry c		X				X		X		X	X						
Clinical Safety Labs d	X	X				X		X		X	X			X	X	X	
Pregnancy test e	X	X														X	
Hepatitis & HIV Screen	X																
12-Lead ECG f	X	X					X				X					X	
Tetanus & VZV antibodies g		X														X	X
PDAI Score		X				X		X		X	X			X	X	X	
PK Sampling h		X	X	X	X						X	X	X	X			
Immunogenicity i		X						X			X					X	
Study Drug Administration j		X				X		X		X	X						
Immunoglobulins (IgG, IgA, IgM) and IgG subtypes (IgG 1-4) k	X	X	X	X	X	X	X	X	X	X	X	X	X	X	X	X	
CIC		X			X	X	X	X	X	X	X			X	X	X	
Anti-Dsg (1 & 3) antibody titer	X	X				X		X			X			X		X	
C3 and AECA l		X						X						X		X	
FCGR2A m		X															
RNAseq m		X						X						X		X	
Urine IgG m		X						X						X		X	
Immune phenotyping n		X									X						
Optional Skin Biopsy		X	X	X				X						X		X	
Photography o		X												X		X	
Adverse Events	To be collected from the date that the ICF is signed until 28 days after last dose of study drug.																
Concomitant Medications	To be collected from within 14 days prior to Day 0 through 28 days after last dose of study drug.																

ECG = electrocardiogram; ET= Early Termination; HIV = human immunodeficiency virus; ICF = informed consent form; PD = pharmacodynamic; PK = pharmacokinetic; VZV = varicella-zoster virus

- 
- a: Complete **PE**, including weight, to be performed. Height and BMI will be additional assessments conducted at screening.

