Safety evaluations will be conducted by a dose escalation committee (DEC). The DEC will consist of the Medical Monitor, an Independent Clinical Expert and a Syntimmune Medical Officer. To assist in the safety assessments, the DEC may request that Investigators, other experts, or members within their organizations review the data and participate in the discussions. Dosing and dose escalation will proceed if the DEC has determined that it would be safe and appropriate to do so. In addition, over the course of the study, the DEC will review any drug-related SAEs to determine if modifications to the study or other measures are necessary to ensure the safety of the subjects.

On days where study drug is administered, vital sign and pulse oximetry measurements will be collected immediately prior to the infusion; 15, 30, and 45 minutes after the start of the infusion; at completion of the infusion; and 30 minutes, 1 hour and 2 hours following completion of the infusion.

On Days 0 and 28, PK blood samples will be collected prior to infusion start and then over the subsequent 48 hours. Subjects will remain at the clinic through the 6-hour PK sample collection and will return to the clinic for the 24- and 48-hour collections. Additional samples will be collected on Days 5 and 33.

On Day 0 photographs will be taken of active lesions. Follow-up photographs will be taken of the same areas on Days 33 and 56. If a subject begins a steroid taper, additional photographs will be taken at the clinic visit during which the decision to begin the taper is made.

Subsequent visits will occur on Days 1, 2, 5, 7, 12, 14, 19, 21, 28, 29, 30, 33, and 42 for safety assessments, study drug dosing, sample collections, and other study procedures.

Subjects also will return to the clinic on Day 56 (28 days after receiving their last dose of study drug) for an End-of-Study/Follow-Up visit.

See [Table 1](#) for a schedule of all study events. To assess safety and tolerability, subjects will undergo physical examinations (PEs; including weight), vital sign measurements, clinical (safety) laboratory tests, AE assessments, concomitant medication assessments, and electrocardiograms (ECG).

**Note:** No vaccinations may be given from within 2 weeks of screening until 2 months following the last dose of study drug.

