#### **6.7.3 Serum Tetanus Antibody and Varicella-Zoster Virus Antibody Testing**

Samples for serum tetanus antibody and varicella-zoster virus antibody testing are to be collected at baseline (pre-dose, Day 0) and on Day 56 (Follow-Up visit). Testing at Day 56 will not be done for any subject whose baseline titer is below the level of detection. Specifically, if the baseline VZV titer is above the detectable level, but tetanus is not, only the VZV antibody titer will be tested on Day 56. If the Day 56 results are below the baseline value, defined as greater than 30% below the baseline value, or if the subject falls below the level of detection, the subject will be re-tested at 1 month after the Follow-Up visit (approximately 2 months after the subject's last dose); if still below the baseline value (or level of detection), the subject will be re-tested after another month (3 months after last dose). Any subject whose baseline value for tetanus or VZV was above the detectable level at baseline, and is not within 30% of the baseline value or is below the detectable level on Day 56 and upon 2 retests (2 and 3 months following last dose of SYNT001), will be referred to their primary care physician for further management.

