### 6.9 Prior and Concomitant Medications

All medications a subject receives within 14 days prior to enrollment through the end of the study (Day 56) will be documented on the source document and eCRF.

Note: No vaccinations may be given from within 2 weeks of screening until 2 months following the last dose of study drug.

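### Tetanus and varicella-zoster titers are re-tested up to 3 months after the last dose, but vaccinations and most immunoglobulin use go unrecorded after Day 56

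*Protocol*

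**What the plan says.** **Recording.** Table 1 gives the concomitant medication window as "To be collected from within 14 days prior to Day 0 through 28 days after last dose of study drug". Section 10 says "All treatments a subject receives within 14 days prior to enrollment through the end of the study (Day 56) will be documented", and Section 6.9 sets the same Day 56 limit.

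**Vaccination.** Section 10 lists vaccinations among the treatments covered by "Use of the following treatments will not be permitted during the study unless otherwise specified", and the synopsis has a matching list. Section 4.3 reads "No vaccinations may be given from within 2 weeks of screening until 2 months following the last dose of study drug". Section 6.9 repeats this, and Section 9.6 states it as an obligation: "Subjects must not receive any vaccinations from within 2 weeks of screening until 2 months after the last dose of study drug".

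**Titers.** Under Section 6.7.3 and note g to Table 1, a subject with a detectable baseline whose Day 56 titer is more than 30% below baseline, or undetectable, is re-tested about two months after the last dose. If the titer is still low, "the subject will be re-tested after another month (3 months after last dose"). A subject who is low on Day 56 and at both re-tests is referred to primary care.

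**Extended visits.** Note q to Table 1 and Section 7.17 provide these visits only for the titer re-tests. In the extended follow-up column of Table 1, the tetanus/VZV row is the only one marked. The last concomitant medication assessment listed in Section 7 is at Day 56.

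**Immunoglobulin.** Section 9.6.2 says IVIG can be given for a bacterial infection while IgG is low. IVIG is not on the Section 10 prohibited list.

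**The concern.** Section 9.6.2 gives the reason for these titers: the drug may lower antibodies left by earlier vaccination. The re-tests show whether a reduced titer comes back. By design they are taken in subjects whose titer was low at Day 56, and a low titer could itself prompt someone to vaccinate.

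If a vaccine or an immunoglobulin product is given between Day 56 and a re-test, the titer can rise because of that product. Nothing scheduled at the extended visit would show this. The value would look like natural recovery, and because referral needs low results at all three time points, one raised titer is enough to keep the rule from being met.

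Section 6.9 shows the mismatch within a few lines: it bans vaccination to two months after the last dose but documents medications only to Day 56. For the last month of its own ban, the planned data cannot show whether the ban was kept.

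**Working it through.** No sample size, power or error rate is involved. The check is calendar arithmetic on the protocol's own days, with one assumption: a month is 28 to 31 days.

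**Inputs**
- Last dose: Day 28 (Section 9.3).
- End of recording: 28 days after the last dose (Table 1), or Day 56 (Sections 6.9 and 10).
- Longer vaccination ban: to two months after the last dose (Sections 4.3, 6.9 and 9.6).
- Re-tests: about two and three months after the last dose (Section 6.7.3).

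**The plan's own figure.** 28 + 28 = 56, so the two ways of stating the end of recording agree.

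**Dates**, with m the length of a month in days:
- End of the two-month ban: 28 + 2m, which is Day 84 (m = 28) to Day 90 (m = 31).
- First re-test: 28 + 2m, again Day 84 to 90. Counted as Day 56 + m, it is Day 84 to 87.
- Second re-test: 28 + 3m, which is Day 112 to 121.

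**Intervals**

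| Interval | Formula | m = 28 | m = 31 |
|---|---|---|---|
| End of recording to last re-test | (28 + 3m) − 56 | 56 days | 65 days |
| Banned under the two-month rule, not recorded | (28 + 2m) − 56 | 28 days | 34 days |
| Neither banned nor recorded | (28 + 3m) − (28 + 2m) | 28 days | 31 days |

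The banned but unrecorded part is 28/56 = 50% to 34/65 = 52% of the interval, so about half.

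The days assume all five doses were given. For a subject who stops early, the same intervals apply when counted from the actual last dose, provided the re-tests follow the same spacing.

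**The case against.** **The ban wording can be reconciled.** A reader might infer that Section 10 and the synopsis, which confine the ban to the study, leave vaccination free from Day 56 and so leave the whole interval unbanned. The documents do not support that. Section 10 makes an exception for what is specified elsewhere, three sections specify two months, and keeping to the longer rule satisfies both texts. This stands. The wording should be aligned, but it is not the heart of the point.

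**A vaccination before the first re-test would be a deviation.** Under the two-month rule the ban ends at about the time of that re-test. Only subjects still low there go on to the second, so only they pass through the month with no ban. This also stands, but a deviation in that period would not be seen at the visit.

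**Some late treatment is still captured.** Events after the reporting period that are judged drug-related are recorded (Section 6.10), with the treatment used (Section 11.3.6). Related SAEs beyond 28 days are reported with therapeutic measures (Section 11.3.9.3). Site source records should note concomitant therapy (Section 17.2). Section 9.6.2 also expects IgG back to normal within four weeks of multiple dosing, from primate data, which is about Day 56. Immunoglobulin for a drug-related infection would therefore be recorded. What remains uncaptured is routine vaccination, and immunoglobulin given for an event not judged drug-related.

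**No analysis depends on it.** The titers are not among the outcome measures in Section 4.2, and no recovery rate is defined. A reader might infer that one vaccinated subject shifts a recovery percentage by a fixed amount. With no such rate and no fixed denominator of re-tested subjects, no figure can be given.

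**A missed referral may do no harm.** If a booster has already restored the titer, the documents show no unmet need. This stands; what is left is the reading of the titer.

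**Conclusion.** The gap is real and narrow. For about 56 to 65 days before the last possible titer, the protocol collects neither vaccinations nor immunoglobulin given for events not judged drug-related. About the first half is banned under the two-month rule but unrecorded; the last 28 to 31 days are neither. A re-test value raised by such a product cannot be distinguished from natural recovery and can stop the referral rule from being met.

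The effect is confined to interpreting individual safety titers in subjects who were low at Day 56. How many that will be is not stated; at most 27 subjects can be enrolled. The primary safety, PK, PD and PDAI analyses are untouched.

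A reader might also infer that the synopsis duration ("Up to 70 days (10 weeks): Screening of up to 2 weeks (14 days"), plus dosing and follow-up) is wrong because it leaves out the extended visits. It is not: 14 + 28 + 28 = 70 days is the planned course to Day 56, and the extended visits are conditional.

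The conclusion rests on the 28 to 31 day month and on the extended visits containing only what Table 1 and Section 7.17 list. It is a cheap improvement that should be made in the protocol, since an analysis plan cannot use exposures that were never collected.

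**What to change.** - In Table 1 and Sections 6.9 and 7.17, extend the recording of vaccinations and immunoglobulin products to the last titer re-test. Other concomitant medication can keep its present window.
- In the listings, flag any titer drawn after such a product, so that it is not read as natural recovery.
- Reconcile the vaccination wording in Section 10 and the synopsis with Sections 4.3, 6.9 and 9.6, so that one end point is stated throughout. Which end point that should be is for the sponsor to settle; this review does not choose it.

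The cost is one question at visits that already take place, and amendment wording. Some titers may be flagged as not interpretable for recovery.
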